11.5.6.2. PGA Classification

Interpretation of no change status in PGA is defined as the following:

- A little better, no change, and a little worse.

A little better and a little worse are considered placebo effect and are treated as no change in PGA status. See for a detailed description of the PGA assessment tool Table 11.5-1

11.5.6.3. CCS Status Classification

Subjects will be classified as improved, unchanged, or worsened by comparing their clinical response in the current visit to their enrollment visit. At the 12 months Clinic Visit, subjects' status will be compared to their status at enrollment. The following criteria will be used:

- Improved: Subjects are considered improved if they experienced a favorable change in at least one NYHA functional class or in the PGA (or both) while remaining alive and free of HF hospitalization comparing to their status in the Enrollment Visit. See Table 11.5-1 on selecting improved PGA status.

- Worsened: Subjects are considered worsened if any of the followings occurs:
 - died (from any cause) or
 - experienced an HF hospitalization or
 - reported worsening of at least one NYHA functional class or
 - reported worsening of the PGA comparing to their status immediately prior to receiving the CRT-D implantation. See Table 11.5-1 on selecting worsened PGA status.

- Unchanged: Subjects are considered unchanged if they are neither improved nor worsened.

11.5.7. Current Device Settings and Status

After initial device interrogation, print a copy of the Combined Report and Settings Report to document current device settings and status prior to conducting any test and changing the programming settings.

11.5.8. Changes in programming since the last Clinic Visit

Collect changes done in programming since the last Clinic Visit:

- Parameters modified and Features enabled/disabled
- Who made the change (investigator, device check facility, emergency services, other)
- Date of the change
- Impact of the change.

11.5.9. SmartDelay test and value

If SmartDelay test done please follow instructions from Section 11.4.11.1

11.5.10. LV VectorGuide test and value

If LV Vector Guide test done, please follow instructions from Section 11.4.11.2

11.5.11. SmartVector and SmartOffset value

If SmartVector and Smart Offset tests done, please follow instructions from Section 11.4.11.3

11.5.12. Current device setting and status

Print a copy of the Quick Notes Report to document current device settings and status prior to conducting any test and changing the programming settings. A list of settings and status, including but not limited to the SmartDelay, Vector Guide, LV MSP and HeartLogic settings, percent of pacing (% RV pacing, %LV pacing), and percent of AT/AF are recommended to be collected (if applicable).

11.5.13. Battery Consumption

The following values are required to be collected:

- Time to explant

11.5.14. Lead Measurements

The lead measurements are recommended to be collected for RA lead, RV lead, and LV lead. Please follow instructions in Section 11.4.10.

11.5.15. Optimization information

Each site should be using Optimization features or any other method to optimize their subjects as per their site SOC. BSC Optimization Features Data (SmartDelay, LV VectorGuide, LV MSP, HeartLogic) need to be collected if they are used as any other optimization method used following instructions in Section 11.4.11.

11.5.16. Final Device Settings and Status

Print a copy of the Combined Report and Settings Report for all subjects at the end of the visit and clear the device counters as the final step.

11.5.17. Adverse Events Assessment

Study required adverse event will be collected and assessed for each eligible subject after signing of the informed consent. See Section 19.1 for Adverse Event data collection and reporting requirements.

A summary of the source documentation required at 12 months Clinic Visit is described in Table 11.5-2.

Table 11.5-2: Source Documentation required at 12 months Clinic Visit

Data Collection Requirement	Retention of Original Source Documentation

 • NYHA Class assessment • Physical Assessment • Cardiac Medication Changes • Patient Global Assessment • Physician Global Assessment • Reportable Adverse Events, HF hospitalizations and Device Deficiencies (if applicable) 	Study Center

 • Echocardiogram data (if available) 	Study Center

 • 12-lead ECG (if available) 	Study Center

 • Device and leads information • Device Settings Report (at the beginning and at the end of the visit) • Device features used report (if applicable) • Device Combined Report (at the beginning and at the end of the visit) 	Printed reports will remain at Study Center

11.6. Additional SOC Clinic Visits

An Additional SOC Visit is recommended to be completed when:

- The Clinic Visit is done within the site SOC for this HF subject population and
- The device is interrogated and any of the programming settings have been permanently changed. A rationale for the setting changes may be collected

The level of data collection during this Additional Clinic Visits will remain as per each site SOC, however the minimum will be to collect device Settings/Features data and Programming. Save a print out of the interrogation, and complete Adverse Event Assessment and report if applicable.

A summary of the source documentation required at Additional SOC Clinic Visit is described in Table 11.6-1.

Table 11.6-1: Source Documentation Required at Additional SOC Clinic Visits

Data Collection	Retention of Original Source Documentation

• NYHA Class assessment (if applicable)• Physical Assessment (if applicable)• Cardiac Medication Changes (if applicable)• Reportable Adverse Events, HF hospitalizations and Device Deficiencies (if applicable)	Study Center

• Device and leads information• Device Settings Report (at the beginning and at the end of the visit)• Device features used report (if applicable)• Device Combined Report (at the beginning and at the end of the visit)	Printed reports will remain at Study Center

11.7. 24 months Clinic Visit, 36 months Clinic Visit and Annual Clinic Visits

For only those subjects belonging to the NG4 PMCF Cohort, the 24 months Clinic Visit, 36 months Clinic Visit and Annual Clinic Visit will have to be performed as per each site SOC. The same procedures and data collection will apply to all visits.

- The 24 months Clinic Visit must be performed at 690-750 calendar days post Enrollment Visit *(Required)*
- The 36 months Clinic Visit must be performed at 1050-1110 calendar days post Enrollment Visit *(Required)*
- Annual Clinic Visit must be performed for all NG4 PMCF subjects until last subject from the PMCF cohort will have complete the 36 months Clinic Visit *(Required)*

Subjects with LATITUDE remote monitoring system may have their device performance and diagnostic data downloaded remotely from the LATITUDE BSC team during these visits timeframe. The device data transmission via LATTITUDE will not be replacing the Clinic Visit.

An overview of data to be collected at 24, 36 months Clinic Visit and Annual Visit is provided below, with further details followed in the sections below.

- NYHA class assessment
- Cardiac Medications Changes
- Current device setting and status
- Lead measurements
- LV MSP feature use and programming (if applicable)
- HeartLogic feature data (if applicable)
- Battery consumption
- Final device settings and status
- Adverse Events Assessment

11.7.1. NYHA Class Assessment

The subject's current NYHA Class must be determined based on Table 11.4-1.

11.7.2. Cardiac Medication Changes

Subject current cardiovascular medications changes from their last study visit (increase, decrease, new or removed). Medications collected include: diuretics, ACE inhibitors/angiotensin receptor blockers, beta blockers, aldosterone antagonists, Nephilysin inhibitors, Class I/III antiarrhythmics, calcium channel blockers, anti-hypertensive drugs, and statins.

11.7.3. Current device setting and status

After initial device interrogation, print a copy of the Combined Report and Settings Report to document current device settings and status prior to conducting any test and changing the programming settings.

11.7.4. Changes in programming since the last Study Clinic Visit

Collect changes done in programming since the last Clinic Visit

- Parameters modified and Features enabled/disabled
- Who made the change (investigator, device check facility, emergency services, other)
- Date of the change
- Impact of the change

11.7.5. Battery Consumption

The following values are required to be collected:

- Time to explant

11.7.6. Lead Measurements

The lead measurements are recommended to be collected for RA lead, RV lead, and LV lead. Please follow instructions in Section 11.4.10.

11.7.7. LV MSP feature Data

Collect information about the LV MSP feature. Please follow instructions from Section 11.4.11.3.

11.7.8. HeartLogic feature Data

For subjects with HeartLogic feature, its usage throughout the follow-up period will be documented along with changes to alert thresholds and review of sensor trends. Please follow instructions from Section HeartLogic feature Data 11.4.11.4.

11.7.9. Final Device Settings and Status

Print a copy of the Combined Report and Settings Report for all subjects at the end of the visit and clear the device counters as the final step.

11.7.10. Adverse Events Assessment

Study required adverse event will be collected and assessed for each eligible subject after signing of the informed consent. See Section 19.1 for Adverse Event data collection and reporting requirements.

A summary of the source documentation required at 24, 36 months and Annual Clinic Visits is described in Table 11.7-1.

Table 11.7-1: Source Documentation Required at 24, 36 months and Annual Clinic Visit

Data Collection Requirement	Retention of Original Source Documentation

• NYHA Class• Medication changes• LV MSP and HeartLogic features data (if applicable)• Reportable Adverse Events, HF hospitalizations and Device Deficiencies (if applicable)	Study Center

• Device and leads information• Device Settings Report (at the beginning and at the	Printed reports will remain at Study Center

end of the visit) • Device features used report (if applicable) • Device Combined Report (at the beginning and at the end of the visit)	
---	--

11.8. Study Completion

Subjects enrolled in SMART Registry only will conclude study participation once the 12 months visit will be performed. However all subjects enrolled also in NG4 PMCF Cohort will complete study participation only when the last enrolled subject in the PMCF will have completed the 36 months Clinic Visit. Sites will continue to follow subjects until notified of follow-up completion. Sites will be notified when subject follow-up at their site is complete for the study.

12. Statistical Considerations

12.1. Endpoints

12.1.1. Primary Endpoint

CRT Response rates will be determined in the entire SMART Registry and in selected subgroups. No formal hypotheses will be evaluated for this analysis. To fulfill post-approval requirements related to the NG4 family of devices, the NG4 PG-related complication free rate (CFR) at 36 months will be evaluated in the subjects included in the NG4 PMCF Cohort. Details of the SMART Registry Primary Objective and the NG4 PMCF Cohort Primary Endpoint are provided in the following sections.

12.1.2. SMART Registry Primary Endpoint

12.1.2.1. Hypotheses

There are no formal hypotheses to be tested for the SMART Registry Primary Objective.

12.1.2.2. Sample Size

Due to a lack of hypotheses for this objective, the sample size cannot be determined through traditional statistical powering techniques. It is, however, desired to have a high degree of confidence in the CRT Response rates obtained in the study. In order to obtain a two-sided 95% confidence interval width of the overall SMART Registry CRT Response rate that does not exceed 5%, a total of 2000 subject enrollments are required. Additionally, it is expected that with a total of 2000 enrollments, each subgroup analysis will include a sufficient sample of approximately 50 subjects.

12.1.2.3. Statistical Methods

The Clinical Composite Score allows for three levels of CRT Response: Improved, Unchanged or Worsened. The number and percent of SMART Registry subjects contributing to each level of CRT Response will be calculated.

CRT Response rates will be compared between selected subgroups. Due to the ordinal nature of the three CRT response levels defined by the Clinical Composite Score, statistical tests accounting for ordinality of response will be used, when appropriate. In analyses comparing two subgroups, a Cochran-Armitage test for trend will be employed. If more than two subgroups will be compared, a cumulative logit model or some other appropriate test will be used.

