MOMENTUM™ X4	G128 and G138	G128 and G138
VIGILANT™ X4	G228, G237, G247 and G248	G228, G237, G247 and G248
CHARISMA™ X4	G328, G337, G347 and G348	Not available

** The NG4 family of CRT-D devices may not be available in the US during a portion of the study. NG4 devices may not be used in the US until device approval is received from FDA.*

Study Design Global, multicenter, prospective, observational, single-arm post market study (Registry)

Planned Number of Subjects Approximately 2000 subjects will be enrolled in the study.
To reduce the impact of individual center bias, each site may enroll up to a maximum of 200 subjects.
NG4 PMCF Cohort will be constituted by a minimum of the first 103 European subjects identified by the Sponsor enrolled in the SMART Registry, implanted with an NG4 device and that had LV MSP feature enabled at any time during the initial 12 months follow up. The actual belonging to the NG4 PMCF study cohort will be based on sponsor's becoming aware date of the MSP feature being enabled, therefore following a chronological order.

Strategic Management to Optimize Response To Cardiac Resynchronization Therapy Registry SMART Registry	
Planned Number of Participating Sites / Countries	A maximum of 200 sites in Europe, United States, Canada and Asia-Pacific region.
Primary Endpoint(s)	CRT Response rate at 12 months, defined by a Clinical Composite Score (Full Registry). 
 ➤ All-cause mortality ➤ Heart failure events ➤ NYHA Class ➤ Quality of life (Patient Global Assessment instrument)
NG4 PMCF Endpoint	The Post Market Clinical Follow Up (PMCF) endpoint is NG4 PG Related Complication Free rate at 36 months (NG4 PMCF Cohort only).
Additional Endpoints	Multivariate analyses to determine which covariates and optimization methods are associated with response (Full Registry)
Method of Assigning Patients to Treatment	Subjects implanted with a quadripolar NG3 or NG4 CRT-D device in conjunction with a quadripolar lead from any manufacturer will be selected based on the inclusion/exclusion criteria and if deemed to be eligible for participation, will be asked to sign the informed consent form. Subjects who meet the eligibility criteria and have signed and dated the Informed Consent Form are considered enrolled in the study.

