5.2. Other Devices

Any commercially available Right Atrial (RA) lead, Right Ventricular (RV) lead and quadripolar LV lead from any manufacturer is eligible in the study.

6. Study Objectives

The primary objective in this study is to learn in a general CRT-D population, which optimization techniques are used and how effective they are. It will compare 12-month response rates among different optimization methods and characterize which selected patient subgroups achieve better response than others.

A subset of SMART Registry subjects will contribute to the NG4 Post Market Clinical Follow-Up (PMCF) Cohort whose objective is collecting data on the NG4 CRT-D features and device usage in a real world setting and monitor long term safety associated with these devices to support CE Mark.

7. Study Endpoints

The primary endpoint will evaluate the CRT Response rate among Full Registry subjects at 12 months, defined by a Clinical Composite Score (CCS) consisting of:

- All-cause mortality
- Heart failure events
- NYHA Class
- Quality of life (patient Global Assessment instrument)

For the NG4 PMCF Cohort the primary endpoint will be NG4 PG related complication free rate at 36 months.

SMART Registry Entire Cohort

The Clinical Composite Score developed by Packer will be evaluated to determine CRT Response in the entire SMART Registry cohort and in selected subgroups^{4, 17}. The CCS will be evaluated at 12 months and consists of all-cause mortality, heart failure events, NYHA class and quality of life as assessed by the patient Global Assessment instruction. CRT response status for each subject will be determined by the CCS, with CRT response classified as improved, unchanged or worsened.

NG4 PMCF Cohort

In the subjects included in the NG4 PMCF Cohort, the NG4 PG-related complication free rate (CFR) at 36 months will be evaluated. The PMCF Primary Endpoint will evaluate the safety of the NG4 device when LV MSP is enabled.

8. Study Design

This is a global, multicenter, prospective, observational, single-arm post market study (Registry), including the NG4 PMCF necessary to support NG4 CE Mark.

8.1. *Scale and Duration*

The study will be conducted at up to 200 sites globally. Approximately 2000 subjects will be enrolled in Europe, United States, Canada and Asia Pacific, and sites may continue to enroll subjects until notified of enrollment completion.

SMART Registry Entire Cohort

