8.2.1. Treatment and Control

Subjects will not be randomized or blinded to treatment received. Any subject meeting all inclusion and no exclusion criteria is enrollment eligible for the SMART Registry. Subjects are considered enrolled in the study once the informed consent form (ICF) has been executed.

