11.4.11. Optimization features information

Each site should be using Optimization features or any other method as per their site SOC.

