12.2.2. Control of Systematic Error/Bias

Several subgroups, multivariate and other analyses are planned to evaluate the primary objective of the SMART Registry. No adjustments to the significance level (i.e., alpha) due to these multiple tests will be made. Rather, interpretation of all results will consider the biological plausibility of the findings as well as the consistency with other results obtained in this study and from other external sources.

The type I error rate for the PMCF Primary Endpoint will be contained at 5% by use of a one-sided 5% alpha in the analysis.

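### Comparing optimization methods needs exposure fixed at enrollment, baseline adjustment and site-robust errors; separately, the site cap is 200 subjects in two places and 20% in a third

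*Combined protocol and SAP*

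**What the plan says.** The primary objective in protocol Section 6 includes the comparison of methods: "It will compare 12-month response rates among different optimization methods". Section 8.2.1 states "Subjects will not be randomized or blinded to treatment received", and Section 11.4.11 leaves the choice of method to the centre: "Each site should be using Optimization features or any other method as per their site SOC". Section 11.5.15 repeats this for the 12-month visit.

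On analysis, the synopsis lists multivariate analyses of covariates and optimization methods under Additional Endpoints. Section 12.2.2 ties them to the main aim: "Several subgroups, multivariate and other analyses are planned to evaluate the primary objective of the SMART Registry". Section 12.1.2.3 names the tests for comparing response: "In analyses comparing two subgroups, a Cochran-Armitage test for trend will be employed"; and "If more than two subgroups will be compared, a cumulative logit model or some other appropriate test will be used". Section 12.3.3 gives an open list of ten baseline covariates, each compared as two subgroups. Optimization method is not on that list. Section 12.3.4 plans a random centre effect, but for the NG4 PMCF endpoint only.

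On the methods themselves:
- Every study device carries VectorGuide and SmartDelay (Section 5.1).
- Multisite pacing (MSP) is a feature of the NG4 family (Sections 5.1 and 5.1.3). NG4 devices may be unavailable in the US for part of the study (note to Table 5.1-1).
- MSP use requires VectorGuide (Section 11.4.11.3).
- Features enabled or disabled since the last visit are recorded with dates (Section 11.5.8).

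On site size, the synopsis allows at most 200 subjects per site, and Section 12.2.3 gives the same number as 10% of expected enrollment. Section 10.4 sets the limit at 20% unless the sponsor approves more in writing.

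**The concern.** The plan announces an adjusted analysis of methods but fixes neither the exposure, nor which covariates enter, nor how site is handled. Each of these can change the reported difference.

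- **Exposure.** The methods are not separate groups: an MSP subject is also a VectorGuide subject. Features can start after enrollment, and Section 4 describes MSP as aimed at patients who do not respond to conventional CRT. If subjects are classified by whether a feature was used at any point before the 12-month assessment, poor response can cause the exposure instead of following it.
- **Case mix.** Section 4 puts response in NYHA Class I-II about 10 points below Class III-IV. Groups that differ in NYHA mix will differ in response with no method effect. MSP use is also tied to device generation and region.
- **Site.** Where method follows centre practice, an interval that ignores site is too narrow.

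There are no formal hypotheses for this objective, so readers will rely on the estimated differences and their intervals.

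**Working it through.** **1. Site cap.** 200/2000 = 10%, which reproduces the figure in Section 12.2.3. The Section 10.4 limit is 0.20 × 2000 = 400, twice as large.

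**2. Late activation under an ever-used grouping.** All inputs are assumed: 60% Improved, no MSP effect, a share e with MSP on at enrollment irrespective of later response, later activation in 5% of the remaining Improved subjects and in a share x of the remaining others.

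- Improved among ever-users = [0.6e + (1−e)(0.6)(0.05)] / [e + (1−e)(0.6×0.05 + 0.4x)]
- Improved among never-users = (0.6×0.95) / [0.6×0.95 + 0.4(1−x)]

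For e = 0.20 and x = 0.10: ever = 0.144/0.256 = 56.3%; never = 0.57/0.93 = 61.3%; difference −5.0 points.

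| e | x | Ever | Never | Difference (points) |
|---|---|---|---|---|
| 0.20 | 0.05 | 60.0% | 60.0% | 0 |
| 0.20 | 0.10 | 56.3% | 61.3% | −5.0 |
| 0.20 | 0.15 | 52.9% | 62.6% | −9.7 |
| 0.20 | 0.20 | 50.0% | 64.0% | −14.0 |
| 0.30 | 0.10 | 57.6% | 61.3% | −3.7 |
| 0.30 | 0.20 | 53.3% | 64.0% | −10.7 |
| 0.10 | 0.10 | 53.4% | 61.3% | −7.9 |
| 0.10 | 0.20 | 43.7% | 64.0% | −20.3 |

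Grouping by status at enrollment gives 0 in every row, by construction.

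**3. Case mix.** From Section 4: two-thirds of Class III-IV respond, Class I-II are 10 points lower, and 80% of Class I-II improve or stay stable. The 80% is assumed for III-IV as well. Improved/Unchanged/Worsened is then 66.7/13.3/20 and 56.7/23.3/20. If the share in Class III-IV differs by d between method groups, the false difference in Improved is 0.10 × d: 1, 2, 3 or 4 points for d of 10, 20, 30 or 40 points (assumed). Cochran-Armitage rejection at nominal 5% is 5.0/5.2/5.4/5.7% with 50 per group, 5.2/5.7/6.6/7.9% with 200 and 5.9/8.6/13.3/20.0% with 1000.

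**4. Site.** Simulation with 200 sites of 10 (2000/200), a 60/20/20 outcome and assumed latent ICC of 0.02/0.05/0.10. A nominal 95% interval for the difference in Improved that ignores site covers:
- 93.7/92.2/88.9% if method is wholly fixed by site (the extreme case);
- 94.0/92.6/90.9% if use is 10% or 90% by site;
- 94.7% to 95.1% if use is balanced within site.

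With 50 per group in 10 sites of 10 and method fixed by site, coverage is 93.7/90.9/87.2%.

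**5. The alternative model.** A proportional-odds fit on method and NYHA class with site-robust errors was simulated with no method effect in 18 scenarios (ICC as above; NYHA imbalance 0, 20 or 40 points; method fixed by site or 10%/90%). It rejects in 4.2% to 6.6% at nominal 5%, against 5.7% to 24.8% for Cochran-Armitage. At 20- and 40-point imbalance the unadjusted odds ratio is 1.07 and 1.13 to 1.14; the adjusted one is 0.99 to 1.01. Its standard error is 1.04 to 1.34 times the naive one.

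**6. Proportional odds.** In step 3 the NYHA odds ratio is (0.667/0.333)/(0.567/0.433) = 1.53 for Improved and 1.00 for Worsened. The assumption can therefore fail and needs a check.

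**The case against.** The plan is not silent. It announces a multivariate analysis, and Section 12.3.3 names the obvious confounders, including NYHA class, etiology, bundle branch block and QRS width. A cumulative logit model can carry covariates and a site term. The registry is exploratory, and Section 12.2.2 says findings will be read for plausibility and consistency. Section 12.3.5 lets changes be documented in an SAP approved before analysis. Every size above except the cap rests on assumed inputs.

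Much of this stands, and it rules out three stronger readings that a reader might infer:
- That no adjustment is planned. The synopsis and Section 12.2.2 say otherwise.
- That methods will be compared by an unadjusted Cochran-Armitage test. Sections 8.3 and 12.1.2.3 permit this, but Section 12.3.3 does not list method among the variables so tested.
- That MSP will be classified as ever used. The first-year activation rule in Section 10.3 defines the PMCF safety cohort, not exposure for the response analysis, and the dated changes in Section 11.5.8 would support a sound definition.

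What does not stand is the idea that nothing needs to change. Reading for plausibility does not remove confounding or reversed timing. Section 12.3.5 offers a route but supplies no definition. Section 12.3.2 allows interim analyses for publications, so the exposure rule could be chosen after results have been seen.

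**Conclusion.** The point holds as a recommendation to settle before analysis. A better analysis than the named tests is available from data already collected. The registry and its overall response rate remain usable without it.

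The definition of exposure matters most. A feature with no effect could appear about 4 to 20 points worse under a grouping that the plan neither adopts nor excludes; the size depends wholly on assumed activation rates. Case-mix bias is 1 to 4 points under the assumed imbalances and barely moves rejection at the planned subgroup size of about 50. Loss of coverage from ignoring site is about 1 to 6 points in the 2000-subject runs (up to 8 with 50 per group) when method is wholly fixed by site, and disappears when use is balanced within site. The documents give no ICC, imbalance or activation rate, so none of these is a prediction.

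The site cap is a plain contradiction, wrong as written, and needs no assumption.

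**What to change.** **(a) Section 12.1.2.3.**
- Make the main comparison of methods a cumulative logit model fitted by GEE with site-robust standard errors.
- Adjust for the Section 12.3.3 covariates required at enrollment: at least NYHA class, age and sex, with the others where available.
- Check proportional odds. If it fails, report separate logistic models for the two splits already listed in Section 12.3.1.
- Define exposure at the enrollment visit with separate, non-exclusive indicators: MSP programmed on at the end of the visit; SmartDelay and VectorGuide as test done at or before the visit. Add a secondary SmartDelay indicator for recommendation programmed.
- Estimate the MSP contrast among NG4 recipients, and analyse later activation separately from the change dates in Section 11.5.8.
- Keep Cochran-Armitage as descriptive, and report results as associations, since site-level confounding can remain.

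Cost: SAP wording and some extra analysis. Intervals were 4% to 34% wider than naive ones in the scenarios run, and fewer subjects enter the MSP contrast. No new subjects, visits or data are needed.

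**(b) Site cap, separately.** Reconcile Section 10.4 with the synopsis and Section 12.2.3 so that one limit applies. Cost: an edit.
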